Cover Page for Clinical Trial Study

Official Title: The Effect of Animal-Assisted Therapy on Prosocial Behavior in Children with Developmental Delay or Autism Spectrum Disorder

NCT #: N/A

Date: November 11, 2024

Study Protocol

Clinical Study Description

The purpose of this study is to investigate the effect of animal-assisted therapy (AAT) on prosocial behavior and emotional regulation, both during and after AAT sessions, in children referred for an autism spectrum disorder (ASD) evaluation or documented developmental delay (DD) or behavioral concerns. We seek to address identified gaps in knowledge of the use of canines in therapy sessions by analyzing short- and long-term effects of AAT and human-animal interaction occurring in AAT sessions. Caregivers were given the option to enroll the child in the AAT study at the follow-up appointment after the diagnostic assessment was completed, or upon enrollment in the ASD program if the child had an ASD diagnosis. Each AAT study lasted between eight to 12 weeks, and caregivers had the option to re-enroll the child for the next study to continue addressing behavioral concerns. Animal-assisted therapy sessions lasted 30 to 45 minutes, depending on the age and ability of the participant. Sessions started with five to 10 minutes of free play with the canine, followed by sensory integration therapy based on the child's identified sensory profile. Participants then entered the clinic room for 20 to 30 minutes of a seated activity in which the therapist, a certified pediatric nurse practitioner (CPNP), taught coping and socialization strategies to participants and caregivers. Sessions concluded with five minutes of play with the canine. Play activities include fetch, soccer, hide and seek, and puzzles. The canine was trained to lay under the table in the clinic room while the therapist was working with the participants. He would provide grounding, light pressure, and deep pressure therapy if the participant became anxious during the sessions. The seated work was recorded using two cameras to ensure visibility of the interactions between the participant and therapist, canine, and caregiver; participant vocalizations and verbalizations; and participant facial expressions. We used two human-animal ethograms to code behavior during sessions and two behavioral assessments to note behavior occurring after sessions. All sessions occurred in the clinic located on the university's campus. Demographic data including participant age, gender, race, ethnicity, referral source, prior medical diagnoses, age of ASD or DD diagnosis, medications, and prior allied health, school, or psychological evaluations. The canine was trained as a therapy dog and was being trained as a service dog at the time of the study. The canine was present during sessions to interact with children and assist them to practice and develop skills to address identified deficits in social-emotional and adaptive functioning, prosocial behavior, and emotional regulation. AAT sessions were recorded to code interactions at a later time.

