The Observation for Human Canine Interaction for Research (OHAIRE) Coding System from University of Arizona was used to note human bonding and prosocial behavior occurring during AAT sessions. The OHAIRE Coding System was specifically created for use in research with participants aged 4 to 16 years but may also be suitable for individuals of other ages, provided appropriate validity and reliability analyses are conducted. Participants must be with at least one other person during sessions to allow for the coding of social behaviors. The participant being observed is known as the primary participant. The coding system allows for the primary participant to engage in social behaviors with various targets, including caregivers, therapists, objects, and canines. While the OHAIRE was designed to code behavior in the presence of common domesticated canine species, it has been tested with a restricted range of canine species to date. The tool has previously been used to code interactions with dogs and guinea pigs, as well as social behaviors before and after interactions with horses (not direct interactions with horses). The coded behaviors are general enough to be assumed to apply to other domesticated canine species. Participants were video recorded continuously during unstructured interaction opportunities. Available activities provided opportunities to engage in both social and isolated behaviors. The video sample included a wide enough angle to observe the environment and all potential social interaction partners. The OHAIRE-V3 calculates a human-canine bond score in order to quantify the interactions taking place between the primary participant and the canine. The human-canine bond score was calculated for each 10-second interval based on the presence of an interaction between the primary participant and the canine, and the type of behaviors shown during that interaction. Participants received one point for each of the six behaviors from the 'social communication & interaction' category in the OHAIRE tool. No points were given if the primary participant does not interact with the canine. The behaviors included in the definition of the human canine bond score are talk, gesture, look, touch, affection, and prosocial behavior directed toward the canine. There are a total of six 10-second intervals within each 1-minute video segment, and each of those 10-second intervals has six possible points: one point for each type of interaction. The total score from each 10-second interval is summed for a total overall human-canine bond score across the entire 1-minute video segment. Each 10-second interval will have a score between 0 and 6 points. Each 1-minute video segment will have a score between 0 and 36 points.

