
The 3-AAT Observation ethogram, adapted with permission from Johns Hopkins University, was used to code both canine and human interaction during AAT sessions. The revised ethogram appraises the frequency of six domains of human interaction (affection, play, care, communication, comfort, withdrawal) and 24 subdomains of human behavior that can occur in an AAT session as seen in Table 1. The ethogram assesses the frequency, intensity, and duration of the interactions between the canine and child. Frequency is measured by a tally count and duration is assessed by rounding either up or down to the nearest 30 second mark. Each interaction has a code for intensity from 0 (not intense) to 3 (the most intense), and the mode of the interaction was entered to run the analysis.

The Strengths and Difficulties Questionnaire (SDQ) is a 25-item tool developed to assess five domains: Emotional Problems, Conduct Problems, Hyperactivity, Peer Problems, and Prosocial. The SDQ is the most used instrument in measuring therapeutic effect of interventions within the emotional state in children and adolescents ages 2 to 18 years, demonstrating reliable internal consistency and validity. The SDQ has two versions, one to be administered at the initiation of therapy and then a follow-up version that includes two additional questions examining the impact of the therapeutic intervention. Scores from four behavioral domains range from zero ("normal") to 10 ("very high concerns"), while Prosocial domain scores are reversed so that 10 indicates "normal" behavior and zero signifies "very high concerns". The SDQ also assesses the total, impact, internalizing, and externalizing scores to provide a complete overview of the child's behavior during the past four weeks. Total scores are the sum of the behavior domains except the Prosocial domains and range from zero (normal) to 40 (very high). Impact scores range from zero (normal) to 10 (very high) and reflect overall distress and impairment interfering with daily social interactions. Internalizing scores reflect the Emotional Problems and Peer Problems domains, while Externalizing scores are the sum of the Conduct Problems and Hyperactivity domains. Both the Internalizing and Externalizing domain scores range from zero (normal) to 20 (very high). The initial SDQ was administered at the beginning of the study and the follow-up assessment was used subsequently every four weeks until the study concluded.

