All interactions between the canine and participants will occur either at the A4A clinic, in the EPLEY Center for Healthcare Professionals, or at the Psychology lab on campus. The first interaction between the canine and the participant will focus on introducing the two and facilitating a bond through play, such as petting or brushing the canine, or throwing a ball. The Purdue University Veterinary College of Medicine O'HAIRE Coding System will be used to observe and code human behavior during this session. Drs. [name] and [name] use a variety of behavioral and developmental evaluations to identify concerns and provide strategies for home therapy to improve delays: 1. Participants ages 8 years and older who are cognitively capable will be asked to self-report their emotional state before and after each AAT session using an 11-point Likert scale chart in the shape of a thermometer, with ranges from "no distress/totally relaxed" to "highest anxiety/stress that you've ever felt." 2. Strengths and Difficulties Questionnaire 3. Positive and Negative Affect Schedule 4. Ages and Stages Questionnaire- 3rd edition 5. Ages and Stages Questionnaire: Social and Emotional - 2nd edition 6. Social-Emotional Assessment Measure 7. Vineland- 3rd edition 8. Social Responsiveness Scale- 2nd edition 9. PEDS: DM-AL 10. Stanford-Binet Intelligence Quota Test Caregiver satisfaction and perspectives of AAT integration in therapy sessions will be assessed via surveys. Demographic data including participant age, gender, race/ethnicity, referral source, prior medical diagnoses, age of ASD or DD diagnosis, medications, and prior allied health or psychological therapies will be collected on all participants. [name] will incorporate AAT into the therapy sessions at the A4A clinic that are guided by the Ages and Stages developmental and social/emotional assessments to target gross and fine motor skill, language, social, and emotional development. Parents will be given handouts that are designed to address deficits identified by the ASQ-3, ASQ:SE-2, and SEAM assessments. The canine will be present to interact with children as they are learning their skill for that week. For example, the canine will interact with the participant while the participant is learning a new skill, such as improvement in handwriting, and the participant will be able to interact and play with the canine if the participant focuses on completing the therapy assignment. Likewise, participants will earn points if they perform their therapy strategies at home and can use those points to interact and play with the canine at their next therapy session. Plush dog toys who look like the canine will be given to pediatric participants as incentive to perform their home therapies. The following data will be collected on the canine: 1. The Canine Behavioral Assessment and Research Questionnaire (C-BARQ), a validated measure to quantify animal behavior during training developed by the University of Pennsylvania in 2003. The C-BARQ database will be used to compare the canine's training progress with other Black Labrador Retriever dogs and can also alert to the onset of behavioral problems so [name] can target these concerns early in the training process. 2. The canine behavior ethogram which assesses 26 canine behaviors during human-animal interactions. The ethogram is divided into three categories: affiliative indicators, moderate stress indicators, and high-stress indicators. The research team will track the number of AAT sessions in which the canine participates each day to assess for variations in temperament and performance. 3. The exact minutes in which canine behaviors are present will be recorded in each AAT session, noting patterns that indicate fatigue or distress. Human-animal interaction will be assessed by: 1. The Purdue University Veterinary College of Medicine O'HAIRE Coding System will be used to observe and code human behavior during AAT sessions. Observable behaviors categories captured by the OHAIRE Coding System include Interactive Behaviors (Social Communication & Environmental Interaction), Emotional Display (Facial, Verbal), and Interfering Behaviors (Aggression, Overactivity, Isolation). The OHAIRE-V3 assessment will be used to calculate a human-animal bond score to quantify the interactions taking place between the pediatric participants and the animal. The ELAN Coding software will be used to achieve high inter-rater reliability through precise timing of observed interactions. All AAT sessions will be recorded after receiving consent from families to retroactively code participant behavior during sessions.

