
- **How long are the procedures likely to take? Include duration and frequency.**

The A4A weekly therapy sessions will last about 30 minutes; however only it is expected that the total HAI time will be approximately 10-15 minutes, depending on the therapy activity. Honors students will assist the canine with [name] during the sessions and will take the canine to [name] office once the HAI part of the appointment has ended.

- **How will information be given to people to get their informed consent to participate in this research? Answers should include specific methods (e.g., verbal consent, information handout, online consent form, full consent form requiring signature documentation.) **Please note that consent materials -- from a script for verbal consent to full consent forms that require participant signature -- must be uploaded in the Notes and Attachments section.**

[name] will contact parents/guardians of potential participants to explain the AAT program and gauge their interest. If interested, parents will come to the A4A clinic on the first floor of ECHP to meet the canine and sign the informed consent form. Verbal assent will be obtained from pediatric patients who are cognitively able to give it.

- **Does data collection rely on a scheduled event, such as a convention or specific date?**

No

- **How will your data be collected? Include all that apply: online, on paper/in person, audio and/or video recordings. **Please note that all data collection materials will need to be uploaded in the Notes and Attachments section. This includes: surveys, questionnaires, interview questions or anything that is given to or asked of a participant.**

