[name]'s lab computers within 24 hours and then immediately deleted from the camcorder device. Video files will be stored on a password-protected computer as password-protected documents.

- **Minimal Risk is defined as risks of harm not greater than those ordinarily encountered in daily life or during the performance of routine physical or psychological examinations or tests. Will participants be exposed to more than minimal risk? Include in your consideration the potential of mental risks if asking sensitive questions, or legal or reputational risks in case of breach of confidentiality.**

Yes

- **Describe the risks in question and any precautions that will be taken to minimize those risks.**

Participants will not be exposed to more than minimal risks while receiving developmental or behavioral evaluations. Participants will be exposed to the canine during therapy sessions for approximately 10 to 15 minutes weekly. The canine will be removed if signs of fatigue, fright, or irritation appear. He will remain on leash throughout the entire AAT session and will be wearing a harness. Honors students will have the canine's leash during the AAT session and will hold him by the harness handle. Also, [name] will assess the disposition of the pediatric participants before allowing the canine to come to the room and will not allow the canine to participate if the pediatric participant's behavior is disruptive or potentially dangerous for the canine.

- **Are there any direct benefits to the participants for participating in this study?**

Yes

- **Describe the benefits participants will or may receive.**

Pediatric participants will receive one plush toy that looks like the canine they are working with.

- **Will the proposed research involve deception or the withholding of information from participants?**

No

- **Will the proposed research necessitate medical clearance from a physician prior to participation?**

No

- **Will the proposed research involve gathering biological samples (blood, tissue, etc.)?**

No

- **Will the proposed research involve administering of substances or providing food and drink, other than water, to participants?**

No

- **Will the proposed research involve physical exercise or conditioning?**

No

- **Does the research require review by a non-UofA IRB?**

No

- **Does this research require approval from another institution or agency, such as a school or privately owned business?**

No

Protocol Number: 2201382953

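### Ethogram tallies and durations have no time denominator, although session length depends on the child's age and ability and the t-tests between verbal groups are unadjusted

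*Combined protocol and SAP*

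**What the plan says.** In the combined protocol and SAP, the Methods paragraph on the 3-AAT Observation ethogram defines the measures: "Frequency is measured by a tally count and duration is assessed by rounding either up or down to the nearest 30 second mark". It adds a 0 to 3 intensity code and says that the mode was entered for analysis. It names no per-minute denominator and no fixed coding window.

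The Clinical Study Description says: "Animal-assisted therapy sessions lasted 30 to 45 minutes, depending on the age and ability of the participant". It puts the seated activity at 20 to 30 minutes and says this part was recorded on two cameras.

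The Statistical Analysis Plan reports 144 sessions, 84 of them recorded and coded. Verbal and nonverbal children are compared on human-animal interaction by independent t-tests, with adjusted degrees of freedom if Levene's test fails, and by Cohen's d with benchmarks of 0.20, 0.50 and 0.80. There is no rate, offset or covariate for observed time, and coded minutes are not among the quantities the plan says it will report.

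**The concern.** A tally over a session is a rate multiplied by the minutes observed, and a total interaction duration builds up with time in the same way. Comparing raw totals tells us about behavior only if observed time is balanced between the groups. Here the stated driver of session length is the child's age and ability, while the grouping variable is verbal ability. Ability is not defined, so a link between the two is plausible but not established.

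Objective 1 asks whether interaction with the dog differs by verbal ability. If one group was coded for longer, its totals would be higher with the same behavior per minute, and both the t-test and d would report that as a verbal-ability difference.

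**Working it through.** **Inputs from the documents.** Seated work 20 to 30 minutes; session 30 to 45 minutes; 84 coded sessions; unadjusted t-tests; Cohen's d. The plan gives no alpha, power, group sizes, event rates or minutes by group, so there is no stated figure to reproduce.

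**Assumptions, not in the documents.** 42 v 42 sessions treated as independent; two-sided 5%; the same mean rate r per minute in both groups, with r from 0.05 to 1 event per minute; a between-session coefficient of variation (CV) of the rate from 0.4 to 0.8; Poisson count noise on top. Mean coded times T1 and T2 are centered on 25 minutes, the middle of the seated range, and differ by 0, 2.5 or 5 minutes.

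**Formulas.** Expected tally m = r × T. Variance v = m + (CV × m)². Then d = (m2 − m1) / √[(v1 + v2)/2]. With equal rates, the ratio of mean tallies is T2/T1.

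**22.5 v 27.5 minutes.** Ratio 27.5/22.5 = 1.22.
- Low end, r = 0.05 and CV = 0.8: m = 1.125 and 1.375; v = 1.125 + 0.81 = 1.935 and 1.375 + 1.21 = 2.585; d = 0.25/√2.26 = 0.17.
- High end, r = 1 and CV = 0.4: m = 22.5 and 27.5; v = 22.5 + 81 = 103.5 and 27.5 + 121 = 148.5; d = 5/√126 = 0.45.

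**23.75 v 26.25 minutes.** Ratio 26.25/23.75 = 1.11.
- Low end: m = 1.1875 and 1.3125; v = 2.09 and 2.415; d = 0.125/√2.2525 = 0.08.
- High end: v = 23.75 + 90.25 = 114 and 26.25 + 110.25 = 136.5; d = 2.5/√125.25 = 0.22.

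**Rejection rates.** Welch t-test on simulated tallies, 20,000 runs per setting, identical behavior per minute in both groups:

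| Mean coded minutes | Ratio of tallies | d | Rejection, raw tally | Rejection, tally per minute |
|---|---|---|---|---|
| 25 v 25 | 1.00 | 0 | about 5% | about 5% |
| 23.75 v 26.25 | 1.11 | 0.08 to 0.22 | about 6% to 18% | about 5% |
| 22.5 v 27.5 | 1.22 | 0.17 to 0.45 | about 11% to 53% | about 5% |

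The last column is about 5% only because sessions are taken as independent.

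**The case against.** **Frequency may not be a t-test outcome.** The only ethogram quantity the plan explicitly says was entered is the mode, most naturally the modal intensity, which does not grow with minutes. The Statistical Analysis Plan does not name the tally. This stands as a condition: the point applies to the extent that tallies or durations were tested. For durations it further requires that they are session totals, since a length recorded per interaction need not grow with session length.

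**Nothing shows that time differed by verbal group.** This also stands. A reader might infer that the comparison is biased; the documents support only that balance is neither ensured nor reported. Equal coded segments per session would remove the problem, but no such rule is stated.

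**Total interaction per session is a legitimate target.** If session length follows ability, some would want the total. That is fair, and it is why the raw tally should be kept alongside the rate.

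**Larger effects are tempting to quote.** Leaving out count noise raises the 22.5 v 27.5 result to 20% to 62%, but a tally has count noise. A reader might also apply a ratio of 1.5 (30/20 or 45/30) to the groups. That needs every session in one group at the short end and every session in the other at the long end, and the ratio depends on what was coded: equal segments give 1.0, and opening play alone (5 to 10 minutes) allows 2.0.

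**The bond score may look equally exposed.** The Methods section says "No points were given if the primary participant does not interact with the canine", and the Human Subjects Protocol Interview says "The canine will be removed if signs of fatigue, fright, or irritation appear" and allows the dog to be withheld from a disruptive child. A reader might infer that absent-dog intervals were scored 0 and pulled one group down. The documents do not support that. The score has a fixed 1-minute base (6 intervals × 6 points = 36), the account of the study as run describes the dog as trained to lie under the table during the seated work, and no absence from coded footage is reported. The withholding and removal rules come from the prospective application. Its plan to record the minutes of canine behaviors concerns fatigue and distress, so it should not be read as a log of when the dog was present.

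**Conclusion.** The point holds as a conditional weakness with a cheap remedy. Raw tallies and total durations are not adjusted for observed time, session length varies with the child's age and ability, and the plan neither fixes nor reports coded minutes by verbal group. A 2.5-minute difference in group means would have little effect in most settings. A 5-minute difference could produce d up to about 0.45, close to the plan's medium benchmark of 0.50, with no difference in behavior. Equal minutes produce no effect.

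These sizes rest on assumed group means, event rates, CV, equal group sizes and independent sessions. They show what unequal time could do and do not estimate what happened in this study. The bond score is a secondary matter that arises only if the dog was out of the coded footage.

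**What to change.** - Take coded minutes from the 84 recordings and report them by verbal group. State whether whole recordings or fixed segments were coded, and which ethogram measures entered the t-tests.
- Analyze ethogram tallies and total interaction durations per coded minute, or model the tally with a log-minutes offset. Keep the raw tally as a sensitivity analysis.
- Secondary: if the dog was out of the coded footage in any 10-second interval, treat that interval as not observable for the bond score rather than 0, with the all-interval score as a sensitivity analysis. If the dog was present throughout, nothing changes.

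**Cost.** No new data are needed. If all seated minutes were coded, one full viewing is at most 84 × 20/60 = 28 to 84 × 30/60 = 42 hours, and less if only segments were coded. The t-tests are then rerun. The main analysis would target a rate instead of total interaction per session, and the report should say so.

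**Limit.** This corrects for observed time only. The application lists 20 children against 84 coded sessions, so sessions repeat within children. Per-minute scoring does not address that dependence, which needs its own analysis.

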Lastly, the Positive and Negative Affect Schedule (PANAS) was administered weekly to measure therapeutic effects occurring in everyday life outside of the AAT session. The PANAS is a 20-item questionnaire utilizing a 5-point Likert scale to assess positive and negative affect occurring the week prior to administration. Each domain has 10 items with scores ranging from 10 to 50, with lower scores reflecting lower levels of positive or negative affect and higher scores signifying higher positive or negative affect²⁹. Total scores on each scale are obtained by adding the scores for each item. Analysis of the PANAS demonstrates very good internal consistency reliability, with alphas ranging from 0.86 to 0.90 for Positive affect and from 0.84 to 0.87 for Negative affect.

Statistical Analysis Plan

This present study used standardized instruments to investigate human-animal interaction (HAI) occurring during AAT sessions and prosocial behavior and emotional regulation demonstrated by participants outside of AAT sessions. SPSS and Microsoft Excel were used to run the analysis. Descriptive statistics were utilized to compare prosocial behavior and emotional regulation occurring apart from AAT sessions between the two groups based on the self-report questionnaires completed by caregivers. A total of 144 sessions were conducted, 84 of which were recorded and coded to analyze HAI during sessions. Independent t-tests were used to analyze the differences in human-animal interaction among children with ASD with varying verbal abilities from the recorded sessions. The homogeneity of the variance (HOV) assumption between two groups was checked using Levene's test for equality of variances in SPSS program before conducting the t-tests analysis. Results of t-tests with adjusted degrees of freedom value were reported if the HOV was violated. The null hypothesis was set to reflect no significant difference in HAI between verbal and nonverbal groups for the independent t-tests; therefore, a significant difference in the human-animal interaction behaviors regarding the children's verbal abilities could be confirmed if the t-test results reject the null hypothesis. Cohen's d was used to report the effect sizes of the independent t-tests; values up to 0.20 were interpreted as small, 0.50 as medium, and 0.80 as large effect size.

Protocol Number: 2201382953
Investigator: [name]

Expiration Date: 03/31/2024
Last Approval Date: 04/01/2023

University of Arkansas System

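### Entering only the mode of the 0 to 3 intensity codes loses precision for that outcome; the mean code, compared at child level, uses the same data better

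*Combined protocol and SAP*

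**What the plan says.** The Methods paragraph on the 3-AAT Observation ethogram names three measures: frequency, intensity and duration. On intensity it states: "Each interaction has a code for intensity from 0 (not intense) to 3 (the most intense), and the mode of the interaction was entered"; the last clause in full is that "the mode of the interaction was entered to run the analysis". The other two are not reduced in this way: "Frequency is measured by a tally count and duration is assessed by rounding either up or down to the nearest 30 second mark". The paragraph does not say over what unit the mode is taken (session, domain, subdomain or child), what is entered when two codes are equally common, or why the mode was preferred.

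The test appears under Design and again in the Statistical Analysis Plan: "Independent t-tests were used to analyze the differences in human-animal interaction among children with ASD with varying verbal abilities from the recorded sessions". Variances are checked with Levene's test, and "Results of t-tests with adjusted degrees of freedom value were reported if the HOV was violated". Cohen's d is the effect size, where "values up to 0.20 were interpreted as small, 0.50 as medium, and 0.80 as large effect size". The data base is given as follows: "A total of 144 sessions were conducted, 84 of which were recorded and coded to analyze HAI during sessions". No separate test is named for intensity, so I read the t-test as applying to it.

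**The concern.** A mean-based test and a mean-based effect size are run on a variable that keeps only the commonest of four codes. The mode of a handful of ordinal codes is unstable. It can be tied, and without a tie rule two analysts with the same codes could enter different values. It also stays put while the rest of the distribution moves, so a group difference in how often interactions are intense can disappear before the test is run.

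Intensity is one of three ethogram measures that serve Objective 1, on whether interaction differs with verbal ability. The study is small and the codes were assigned interaction by interaction, so the information was already collected and is dropped only at the summary step.

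**Working it through.** **Inputs.** From the documents: a four-level code; six domains and 24 subdomains (Methods); 84 coded sessions of 144 (Statistical Analysis Plan); 20 children (Subjects table in the Protocol Summary). Not in the documents, and therefore assumed: two-sided alpha 0.05, a 42 vs 42 split of sessions, the number of codes per unit, their distribution, and their within-session correlation on a latent scale. The plan gives no power or sample-size figure to reproduce.

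**1. What the mode cannot see (no assumptions needed).** Take shares for codes 0, 1, 2, 3.
- 40/30/20/10%: mode 0; mean = 0.3×1 + 0.2×2 + 0.1×3 = 1.0; share coded 2 or 3 = 30%.
- 40/10/20/30%: mode 0; mean = 0.1×1 + 0.2×2 + 0.3×3 = 1.4; share coded 2 or 3 = 50%.

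The share of code 3 triples and the analysed value does not change.

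**2. One set-up in detail.** A latent normal intensity is cut at -0.5, 0.5 and 1.2 into codes 0 to 3. The group shift is 0.3 SD, ties go to the lowest code, sessions are treated as independent, and a Welch t-test is run on 4,000 data sets per cell.

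| Codes per session | Correlation | Power, mode | Power, mean | Loss (points) | Sessions with a tied mode |
|---|---|---|---|---|---|
| 5 | 0.1 | 44% | 68% | 24 | 31% |
| 5 | 0.3 | 38% | 52% | 14 | 26% |
| 10 | 0.1 | 57% | 85% | 28 | 19% |
| 10 | 0.3 | 43% | 60% | 17 | 16% |
| 20 | 0.1 | 69% | 94% | 25 | 12% |
| 20 | 0.3 | 48% | 64% | 16 | 9% |

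Breaking ties at random changed the power of the mode by at most about 3 points. At correlations of 0.5 to 0.7 the loss with 5 to 20 codes fell to about 3 to 10 points. With one code per unit it was zero, with two codes 4 to 9 points, and with three codes 5 to 24. If the mode is taken per domain, 5 to 20 codes per session average 5/6 = 0.8 to 20/6 = 3.3 codes per domain, which is the low end.

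**3. A wider grid.** 2 sample sizes (42 vs 42, 10 vs 10) × 4 code distributions (even, low-skewed, mid-peaked, strong floor) × 4 correlations (0.1 to 0.7) × 5 counts (3 to 40 codes) = 160 scenarios, 3,000 replicates each. The shift was set so that the mean had about 80% power. The mode had less power in all 160. The loss ran from 5 to 78 points, median 15: below 15 in 76 scenarios (47.5%), 15 to 30 in 48 (30%), above 30 in 36 (22.5%). At 42 vs 42:

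| Distribution | Loss at correlation 0.1 | Loss at correlation 0.7 |
|---|---|---|
| Even | 16–21 | 5–8 |
| Low-skewed | 29–37 | 5–10 |
| Mid-peaked | 30–36 | 7–9 |
| Strong floor | 42–76 | 12–15 |

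At correlation 0.3 and 3 to 20 codes, the mode was not unique in about 3 to 28% of units. The squared correlation of mode with mean was 0.40 to 0.75, so by that measure 1 - 0.75 = 25% to 1 - 0.40 = 60% of the information in the mean is lost. With independent units and no true difference, the t-test on the mode rejected in 4.2 to 5.8% of data sets.

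**4. Repeated sessions.** If the count of 20 children applies, 84/20 = 4.2 coded sessions per child on average, so sessions are not independent. Assume 10 vs 10 children, child-level correlation 0.1 to 0.3, session correlation 0.1 and 2 to 20 codes.
- Session-level t-test, no true difference: false positives of about 8 to 23% with the mode and 11 to 29% with the mean. With 5 codes and child correlation 0.2, the rate was 14.8% with the mode and 20.8% with the mean.
- t-test on child averages: error stayed near 5%. Power was about 14 to 33% with the mode and 15 to 41% with the mean, a loss of about 1 to 10 points. The mean was ahead in every cell with two or more codes.

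**The case against.** The strongest reply is that the loss may be small here. The documents give no distribution, count or correlation of codes. Split across six domains, there may be only one to three codes per unit, and codes from one child in one session may agree closely. Once children rather than sessions are the unit, the gain is at most about 10 points and absolute power is low either way. All of this stands, and it is why no single figure can be attached to the point.

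A second reply is that the mode suits ordinal data and the mean assumes equally spaced codes. That would carry weight if the mode were then analysed as ordinal. The t-test and Cohen's d already assume equal spacing.

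A third is that the mean, placed in the session-level t-test as planned, makes matters worse. This is correct. A more precise session summary exposes more of the uncorrected correlation within child, so the summary and the unit of analysis must change together.

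A fourth is that the text is in the past tense and the analysis appears finished, so a new summary would be chosen after the fact. That also stands and governs how the mean should be labelled.

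**Conclusion.** The point holds as a loss of precision and a gap in definition for the intensity outcome. The direction is firm: the mode had less power than the mean in every scenario with several codes per unit. The size is not fixed by the documents. It is zero with one code per unit, a few points when codes are consistent within a unit or child averages are tested, and 15 to 30 points or more with many weakly correlated codes, most of all with a strong floor. These ranges rest on the assumed distributions, counts, correlations, shifts and group splits.

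A reader might infer three stronger things that the documents do not support:
- That the mode costs a set 15 to 30 points of power. Only 30% of the assumed scenarios fall in that band, and the documents do not say which scenario applies.
- That most of the information is discarded. Against the mean, the share was about 25 to 60% at correlation 0.3, and more than half only with a strong floor.
- That the mode creates false positives or undermines the human-animal interaction results as a whole. With independent units its error rate was nominal, and frequency, duration and the OHAIRE bond score are not reduced to a mode. The inflation under repeated sessions comes from the session-level test, not from the mode.

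This is a worthwhile, inexpensive improvement and not a fatal flaw.

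**What to change.** In the Methods paragraph on the 3-AAT ethogram, replace the clause "the mode of the interaction was entered to run the analysis" with text along these lines:

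> For each session, intensity is the mean of all 0 to 3 codes (per domain where there are enough codes). The share of interactions coded 2 or 3 is reported alongside it. Verbal and nonverbal groups are compared on child-level averages, or in a mixed model with a random effect for child.

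Amend Design and the Statistical Analysis Plan to match, so that the mean does not enter the session-level t-test. If the mode results have already been produced, report both and label the mean as a post hoc re-analysis. Wherever the mode is still reported, state the unit over which it was taken and how ties were resolved.

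No new data collection is needed; the cost is a recalculation from codes already recorded, provided the interaction-level codes were kept. The mean assumes equally spaced codes, as the t-test on the mode already does; the share coded 2 or 3 does not need that assumption.
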